5.7.6 Ventilation - specific information

Ventilation - specific information baseline assessment will be summarized by treatment and overall. Information on the assessment (performed/not performed) will be reported, with reasons in case of not execution. The following information will be reported:

Standard/Forms/Template				
Title		Statistical Analysis Plan Template		
Code		Version	Effective Date	Page
PPD		01	29 Aug 2022	41 of 78

- Use of neuromuscular blocking agents (Yes, No)
- Use of inhaled vasodilators (Yes, No)
- Use of the modality of prone positioning (Yes, No)
- Vasoactive medications (Yes, No)
- Sedation (Yes, No)

6. Evaluation of Treatment Compliance and Exposure

6.1 Compliance to study drug and treatment

The assessment of patients' compliance to the IMP will be made by determining the number of tablets administered. On a per patient basis, the evaluation of the compliance will be done using the following formula:

$$\text{Compliance (\%)} = \frac{\text{total number of tablets taken during the treatment period}}{\text{total number of tablets scheduled during the treatment period}} \times 100$$

where "total number of tablets taken during the treatment period" is the sum of number of tablets taken during each day, while the "total number of tablets scheduled during the treatment period" is given by the number of total scheduled tablets, considering that each patient takes 2 tablets three times daily (6 tablets daily) for up to 21 days or until early treatment discontinuation/completion. A fourth daily administration may also be possible for subjects having the drug intakes 6h apart.

The determination of the total number of tablets scheduled during the treatment period starts with the date and time of the 1st IMP intake, and ends with the date and time of the last IMP intake. Details for derivation are reported in section 11.1.1 .

Compliance will be summarized by treatment and overall, by means of summary statistics. In addition, compliance to IMP will also be presented for the following categories: <80%, ≥80%.

Compliance will be presented on FAS and SAF sets.

6.2 Exposure to study drug

The extent of exposure to IMP in days will be summarized with descriptive statistics by treatment group. The extent of exposure (days) will be calculated using:

Extent of exposure (days) = Date of last administration of IMP – Date of first administration of IMP + 1.
Exposure will be tabulated on the FAS and SAF set.

A listing will be provided as well including all data on the study drug administrations.

7. Evaluation of Efficacy

Standard/Forms/Template				
Title		Statistical Analysis Plan Template		
Code		Version	Effective Date	Page
PPD		01	29 Aug 2022	42 of 78

7.1 Analysis of primary endpoint

7.1.1 Analysis details

7.1.1.1 Change in OI from baseline to day 7 of treatment

Summary statistics will be provided for the variable and by subgroups defined in section 4.5. For the estimand definition, please refer to section 4.4.1, while for the derivation of the endpoint please refer to section 11.1.1. Summary statistics will include imputed values at Day 7 for patients who die or are extubated, as defined in section 11.1.1.

The change in OI from baseline will be analyzed by means of an ANOVA adjusting by pre-defined factors (treatment, baseline value of the variable, gender, age class (<65, >=65 years) as fixed effect and site as random effect). In the case baseline value for OI is missing, data will be imputed as described below.

If convergence is not reached or the Estimated G-matrix is not positive definite in at least one of the models after imputation, the random effect will be dropped.

Check of the normality assumption will be performed on change from baseline data, before applying imputation process. As per section 4.1, Normality checks (based on visual inspection and statistical tests) are to be performed on observed data and – in case normality on observed data is not met – also on logarithmic scale. When performing normality checks on logarithmic scale, the checks will be performed on the logarithm of the change from baseline, derived as $\log(\text{OI at day 7}) - \log(\text{OI at baseline})$.

If assumption of normality is not confirmed (see section 4.1) analysis on original scale will be kept. An additional supplementary analysis on log-transformed data (on observed data i.e., not on change from baseline) will also be performed (see section 7.1.3.4).

In case of missing baseline OI, a MI approach will be implemented to impute it.

A MI regression model based on Markov Chain Monte Carlo (MCMC) will be created by including treatment, gender, age class (<65, >=65 years), baseline OI and Day 1 OI as covariates. A thousand data sets will be generated. The random seed number will be **CCI**. Details are provided below.

For the imputation of Day 7 missing data, rules described in section 0 will be applied, and following the estimand definition, for missingness due to treatment discontinuation or any other reason (whichever the reason), MI-RD regression model will be created by including treatment, OI baseline value (imputed as described in this section), gender and age class (<65, >=65 years) as covariates (further details about the MI process are described below).

If there are not enough retrieved dropouts for convergence of MI-RD regression model, the Copy Reference approach will be used using OI baseline value, gender and age class (<65, >=65 years) as

Standard/Forms/Template				
Title		Statistical Analysis Plan Template		
Code		Version	Effective Date	Page
PPD		01	29 Aug 2022	43 of 78

covariates. Imputation of values in the two treatment arms will be done using the non-missing values from all the patients in the control group. The final decision on the use of the MI-RD vs Copy-Reference will be done at the time of the analysis and reported in the CSR.

Whether for MI-RD or Copy-Reference approach, the adjusted estimated changes from baseline for each treatment arm together with the corresponding 95% confidence intervals will be shown. The difference between Reparin and placebo in the change from baseline at Day 7 will be displayed together with the corresponding two-sided 90% confidence interval (in order to reflect the one-sided 95% confidence intervals). One-sided p-value (alpha=0.05 one-sided) will also be displayed for descriptive purpose.

MI process will be implemented as follows:

STEP1: Run MI for OI baseline missing data on 1000 imputations using:

CCI

Use numeric variable in the MCMC model.

At the blinded DRM, a discussion on the pattern of missingness will be held and it will be evaluated if data show a monotone pattern. If it will be evaluated that no monotone pattern is there, the statement “impute=monotone” will be deleted from the SAS code.

STEP 2: A MI-RD for Day 7 missing data will be performed on the output datasets created in step 1 (with “nimpute=1”). A thousand datasets will be generated. The random seed number will be CCI. Missing OI data at Day 7 will be imputed using the specified MI regression model. MI regression model will include treatment, OI baseline value (as described in step 1), gender and age class (<65, >=65 years) as covariates. According to MI-RD approach, only non-missing values from retrieve dropouts will be used to inform the MI regression model.

STEP 3: Derive change from baseline (using imputed/non imputed data).

STEP 4: Each of the 1000 datasets with observed and imputed data will be analyzed using the ANOVA model.

STEP 5: Rubin’s rule will be used for combining results to draw inference.

Standard/Forms/Template				
Title		Statistical Analysis Plan Template		
Code		Version	Effective Date	Page
PPD		01	29 Aug 2022	44 of 78

7.1.1.2 VFD at day 28

Summary statistics will be provided for the variable and by subgroups defined in section 4.5. For the estimand definition, please refer to section 4.4.1, while for the derivation of the endpoint please refer to section 11.1.1.

VFD at day 28 will be analysed using an ANOVA model as described in section 7.1.1.1 (considering as covariates: treatment, gender and age class (<65, >=65 years)).

If convergence is not reached or the Estimated G-matrix is not positive definite in at least one of the models after imputation, the random effect will be dropped.

Check of the normality assumption will be performed on the observed data, before applying imputation process.

If assumption of normality is not confirmed (see section 4.1) analysis on original scale will be kept. An additional supplementary analysis on log-transformed data will also be performed (see section 7.1.3.4).

For the imputation of ventilatory free days missing data at day 28, rules described in section 0 will be applied, and following the estimand definition, for missingness due to treatment discontinuation or any other reason (whichever the reason), MI regression model will include treatment, gender and age class (<65, >=65 years) as covariates. A thousand data sets will be generated. The random seed number will be **CCI**. MI will be implemented in the following steps:

1. Missing data at Day 28 will be imputed using the specified MI regression model. According to MI-RD approach, only non-missing values from retrieve dropouts will be used to inform the MI regression model. A total of 1000 datasets will be created. These datasets will be utilized in Step #2.
2. Each of the 1000 dataset with observed and imputed data will be analyzed using the ANOVA model. Rubin's rule will be used for combining results to draw inference.

If there are not enough retrieved dropouts for convergence of MI-RD regression model, the Copy Reference approach will be used using gender and age class (<65, >=65 years) as covariates. Imputation of values in the two treatment arms will be done using the non-missing values from all the patients in the control group. The final decision on the use of the MI-RD vs Copy-Reference will be done at the time of the analysis and reported in the CSR.

The difference between Reparixin and placebo at Day 28 will be displayed together with the corresponding two-sided 90% confidence interval (in order to reflect the one-sided 95% confidence intervals). One-sided p-value (alpha=0.05 one-sided) will also be displayed for descriptive purpose.

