CC1 and its objective was to evaluate efficacy and safety of oral reparixin as compared to placebo (both on top of standard treatment). From February 2021 to June 2021, patients with RT-PCR-confirmed severe COVID-19 were randomized in a 2:1 fashion to receive oral reparixin 1200 mg (2x 600 mg tablets) three times a day (TID) or placebo for 21 days. The treatment schedule and regimen were consistent with the previous trial. Follow-up information on the patients' clinical condition and survival were collected until day 90. Briefly, patients were considered for inclusion if they had evidence of respiratory failure requiring oxygen support (i.e., PaO₂/FiO₂ ratio between 100 and 300, SpO₂ <95% at room air, or respiratory rate (RR) ≥24 breaths/min at room air), abnormal chest imaging, and laboratory signs of inflammation (LDH >normal range, CRP ≥100 mg/L or IL-6 ≥40 pg/mL, serum ferritin ≥900 ng/mL, XDP >20 mcg/mL). The primary efficacy outcome was the proportion of patients alive and with no respiratory failure at day 28, defined as no need for invasive mechanical ventilation (IMV), extracorporeal membrane oxygenation (ECMO), or admission to the intensive care unit (ICU) due to worsening respiratory status. Among 279 randomized patients, all enrolled in Europe, 182/185 (98.4%) in the Reparixin group and 88/94 (93.6%) in the placebo group received at least one dose of the investigational product. All participants had a positive RT-PCR assay for SARS-CoV-2 RNA from the upper respiratory tract. At baseline, the cohort was well-balanced across the two groups: mean age 60.8 (SD=11.9) years, 73% were males, 27% were of Hispanic origin, and 30% had a BMI>30 Kg/m². All participants had the typical features of acute respiratory failure i.e., need for oxygen therapy either in the form of low flow supplemental oxygen or high flow nasal cannula (NHNC)/non-invasive ventilation (49.2% in the reparixin and 50.0% in the placebo group required HFNC/NIV), with a mean PaO₂/FIO₂ ratio of 200.2 (SD=67.5). The treatment was discontinued more frequently in the placebo group (34 patients [18.4%] vs. 20 [21.3%]), with good compliance to study medication during treatment in both arms (median 97.22% in the reparixin group and 96.85% in the placebo group). According to the Intention-to-Treat (ITT) principle, all randomized and treated patients were considered for the efficacy analysis, using retrieved dropouts' information to handle missing data at Day 28. CC1

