4.1. INCLUSION CRITERIA

To be eligible for inclusion into this study, each patient must fulfill the following inclusion criteria:

1. Signed Informed Consent, according to local guidelines and regulations.
2. Male and female adults (≥ 18 years old).
3. Mechanically ventilated (invasive) patients with $\text{PaO}_2/\text{FIO}_2$ ratio ≤ 200 in the presence of PEEP of ≥ 5 cm H₂O.
4. Respiratory failure not fully explained by cardiac failure or fluid overload (if acute Congestive Heart Failure exacerbation is identified as part of the clinical picture this should be addressed effectively and as soon as possible before the patient can be enrolled).
5. Bilateral radiologic opacities consistent with pulmonary edema on the frontal chest x-ray (CXR) radiograph, or bilateral ground glass opacities on a chest CT scan.
6. ≤ 48 hours from fulfilling above ARDS criteria (if a patient is transferred from a non-participating hospital to a participating site, a 12-hour period beyond the 48 hours is allowed)
7. Females of child-bearing potential who are sexually active must be willing not to get pregnant within 30 days after the last Investigational Medicinal Product (IMP) dose and must agree to at least one of the following reliable methods of contraception:
 - Hormonal contraception, systemic, implantable, transdermal, or injectable contraceptives from at least 2 months before the screening visit until 30 days after the last IMP dose;
 - A sterile sexual partner;
 - Abstinence.

For patients unable to personally consent to the above, due to complications of acute illness and/or its treatment, assurances for the above must be given by LR and reiterated by the patient when/if she is able to do so.

Female participants of non-child-bearing potential or in post-menopausal status for at least 1 year will be admitted. For all female subjects with child-bearing potential, pregnancy test results must be negative before first drug intake.

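### Age enters both co-primary models and all imputation models only as under 65 or 65 and over; entering it in years would be expected to shorten the intervals by about 0.2% to 3.5% at no cost

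*SAP*

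**What the plan says.** SAP Section 7.1.1.1 analyses the change in OI to Day 7 with treatment, baseline OI, gender and "age class (<65, >=65 years) as fixed effect", plus site as a random effect. Section 7.1.1.2 uses the same type of model for VFD, "considering as covariates: treatment, gender and age class (<65, >=65 years").

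The imputation models use the same two classes:

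- Baseline OI (MCMC, Section 7.1.1.1): "including treatment, gender, age class (<65, >=65 years), baseline OI and Day 1 OI as covariates".
- Day 7 OI from retrieved dropouts (MI-RD, Section 7.1.1.1, Step 2): "MI regression model will include treatment, OI baseline value (as described in step 1), gender and age class (<65, >=65 years) as covariates".
- VFD from retrieved dropouts (MI-RD, Section 7.1.1.2): "MI regression model will include treatment, gender and age class (<65, >=65 years) as covariates".
- Fallback for VFD (Section 7.1.1.2): "the Copy Reference approach will be used using gender and age class (<65, >=65 years) as covariates". The OI fallback adds baseline OI to the same terms.
- The missing-at-random sensitivity analysis (Section 7.1.2.1) repeats these covariates.

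Age in years is recorded (Protocol Section 6.5) and summarised (SAP Section 5.4). SAP Section 4.5 uses the 65-year cut for the age subgroup. Protocol Section 9.5.1.1 leaves the choice of baseline factors to the SAP, and the SAP gives no reason for grouping age.

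**The concern.** A two-level class gives a patient of 25 and a patient of 64 the same contribution from age. If outcome changes gradually with age, part of what age could explain stays in the residual. For VFD, age class and gender are the only patient-level covariates besides treatment.

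What is at stake is precision. The trial states no hypothesis, and its sample size is justified only by the expected width of the interval for the group difference (Protocol Section 9.1, SAP Section 3.3). Age in years uses one parameter, as the class does, and needs no new data.

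**Working it through.** **The plan's own precision figure.** The documents give no figure for the effect of grouping age. They do give a margin of at most 46.5% of the SD for a one-sided 95% interval with 60 evaluable patients. The unadjusted half-width with 30 per arm is t(0.95; 58 df) × √(2/30) = 1.672 × 0.258 = 0.432 SD, which is within that limit. The target is therefore met before any covariate is used.

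**Inputs that must be assumed.**

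- Age distribution: the only one in the documents is "mean age 60.8 (SD=11.9) years", from the sponsor's COVID-19 trial (Protocol Section 2.5). That is a different population: its patients were on supplemental oxygen or non-invasive support, and here they are intubated. I therefore use mean 58 to 61 and SD 12 to 16.
- Partial correlation r of age with outcome, given the other model terms: not in the documents. I use 0.1 to 0.4.

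**Step 1: share of a linear age effect kept by the cut.** For normal age, retained share k = φ(c)² / [p(1 − p)], where c = (65 − mean)/SD and p = P(age ≥ 65).

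| Mean, SD | c | φ(c) | p | k |
|---|---|---|---|---|
| 60.8, 11.9 | 0.353 | 0.375 | 0.362 | 60.8% |
| 58, 12 | 0.583 | 0.337 | 0.280 | 56.2% |
| 58, 16 | 0.438 | 0.363 | 0.331 | 59.4% |
| 61, 12 | 0.333 | 0.377 | 0.369 | 61.1% |
| 61, 16 | 0.250 | 0.387 | 0.401 | 62.2% |

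The range is 56% to 62%. Under these assumptions the share cannot exceed 63.7%, reached when the median age is 65. A younger population does worse: mean 50 with SD 15 keeps 43.9%. Eligibility starts at 18 ("Male and female adults (≥ 18 years old"); simulation with age truncated to 18 to 95 years changes the loss at mean 60.8 only from 39.2% to 39.0%.

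**Step 2: effect on the interval.** Ratio of widths, years to class = √[(1 − r²)/(1 − k r²)], with k = 0.608. Equivalent patients = 60 × [(1 − k r²)/(1 − r²) − 1].

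| r | Ratio | Interval shorter by | Equivalent patients of 60 |
|---|---|---|---|
| 0.1 | 0.998 | 0.2% | 0.2 |
| 0.2 | 0.992 | 0.8% | 1.0 |
| 0.3 | 0.981 | 1.9% | 2.3 |
| 0.4 | 0.965 | 3.5% | 4.5 |

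At r = 0.3, taking the unadjusted half-width of 0.432 SD and the plan's SDs, the gain is 0.0188 × 0.432 × 11.5 = 0.09 OI points and 0.0188 × 0.432 × 8 = 0.065 VFD days.

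**Step 3: other shapes of the age effect** (simulated at mean 60.8, SD 11.9; share of the age signal lost).

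| True shape | Lost by class | Lost by linear age |
|---|---|---|
| Linear | 39% | 0% |
| Quadratic | 35% | 3% |
| Exponential | 41% | 14% |
| Logistic | 32% | 4% |
| Linear rise above 50 | 30% | 7% |
| Linear rise above 65 | 48% | 39% |
| Step at 75 | 77% | 63% |
| Step at 65 | 0% | 39% |

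Linear age loses less than the class in every shape tried except a true step at 65.

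**The case against.** Using a pre-specified class that matches the subgroup cut is common and defensible. The inference is declared descriptive, the precision target is met without covariates, and nothing in the documents says how age relates to either endpoint. With a true step at 65, the present model would be the better one. For OI, baseline OI, gender and site may already absorb much of the age effect, which points to the lower end of the r range. All of this stands, and it keeps the point minor.

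A reader might infer three stronger things that the documents do not support:

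- **That about 40% of precision is lost.** The 39% is a share of whatever age explains, and only for a linear effect and that one age distribution. The effect on interval width is far smaller.
- **That the treatment comparison is biased.** Randomisation protects it whichever form age takes.
- **That the imputation is materially weakened.** MI-RD is informed only by retrieved dropouts, whose number is not given, so no gain there can be quantified. If all of them fell in one age class, the class effect could not be estimated; with p = 0.362 the chance is 0.638⁵ + 0.362⁵ = 11% for five such patients and 3% for eight. Age in years avoids that particular failure, but gender and treatment can still cause it.

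Two passages might seem to settle the matter already. The instruction in Section 7.1.1.1 to use a numeric variable in the MCMC model most likely concerns coding, since the covariate named there is still the class. Section 7.1.3.5 allows further covariates in a supplementary analysis but does not replace the class in the primary one.

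**Conclusion.** The point holds as a minor efficiency improvement. Age enters both co-primary models and all imputation models only as a class, although exact age is available. Under a roughly linear effect and normal age with mean 58 to 61 and SD 12 to 16, the class keeps about 56% to 62% of what age explains. Entering age in years is then expected to shorten the interval by about 0.2% to 3.5% for partial correlations of 0.1 to 0.4. The age distribution, the linear shape and the correlations are all assumptions. The validity of the comparison and the stated precision target are not affected. The change is worth making because it costs nothing in a trial whose size rests on precision alone.

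**What to change.** Replace the two-level age class by age in years, as a continuous covariate, in:

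- the OI and VFD analysis models (SAP Sections 7.1.1.1 and 7.1.1.2);
- the baseline-OI MCMC model (Section 7.1.1.1);
- the MI-RD and Copy Reference models for both endpoints (Sections 7.1.1.1 and 7.1.1.2);
- the missing-at-random models (Section 7.1.2.1).

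Carry the wording into the per-protocol fallback in Section 7.1.3.3, which removes age if models do not converge. Keep the class only to define the age subgroup. Section 4.5 now drops the covariate that belongs to a subgroup; state whether continuous age is dropped or kept within the two age subgroups.

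The cost is SAP wording: no new data, no extra parameter and, since Protocol Section 9.5.1.1 defers the factors to the SAP, no change to that protocol text. If the blind is already broken, leave the primary models as they are and report continuous age as a labelled supplementary analysis.

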3.3 Sample size justification

The sample size of the study is calculated based on results from literature [5-8]. Evaluation of the efficacy for this study is being accomplished through estimation of a 95% confidence interval. No hypotheses are specified for this study and no p-values are being calculated but for descriptive purposes, therefore no level of significance is specified.

Considering a randomization ratio 1:1 (reparixin vs. placebo), a sample size of 60 evaluable subjects is considered adequate for assessing the difference between groups in primary endpoints, i.e., change from baseline in OI at day 7 and VFD at day 28.

The given sample size will provide a reasonable precision in the estimation of group differences in primary endpoints to an expected margin of error for a 95% one-sided confidence interval of at most 46.5% the standard deviation, whatever it is:

Standard/Forms/Template				
Title		Statistical Analysis Plan Template		
Code		Version	Effective Date	Page
PPD		01	29 Aug 2022	20 of 78

- Assuming a standard deviation of 11.5 points for OI, the 95% one-sided confidence interval for the difference between groups will have a width of 5.35 points;
- Assuming a standard deviation of 8 days for VFD, the 95% one-sided confidence interval for the difference between groups will have a width of 3.75 days.

If 10% of enrolled patients will not be evaluable for primary analysis, the total number of patients to be enrolled will be approximately 66.

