3.4 Randomization and blinding

3.4.1 Randomization

Enrolled patients will be randomized in a 1:1 ratio to either reparixin or placebo according to the stratified randomization list. Dropouts after randomization will not be replaced.

The permuted block randomization list will be generated with a computer procedure by a CRO independent statistician not involved in the conduct of the study and will be provided to Dompé in a sealed envelope to prevent unblinding. The facility responsible of IMP packaging/labelling will also receive appropriate randomization codes for the purpose of IMP preparation.

Randomization will be performed through Interactive Response System (IRS). Each Patient Kit number will be randomly associated with a treatment group. Access to individual patient treatment code will be allowed only in the event of a medical emergency where the knowledge of patient treatment is required to provide the patient with appropriate care. The investigator and Dompé Pharmacovigilance will have access to the randomization code for a specific patient in case of a medical emergency or for safety reasons. Unblinding events will be recorded and reported in the Clinical Study Report (CSR). The treatment assignment information will be kept confidential and will not be disclosed to any other.

Once the study has been completed and the database has been locked, the treatment assignment information will be accessible to the study biostatistician(s) who will perform the statistical analyses and will generate reports.

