3.4.1.1 Stratification factors

Randomization list will be stratified by site. Site is also included in the statistical model, as random effect, for the analysis of the primary efficacy endpoints (section 7.1.1.1)

Given the high number of sites and the relatively small number of patients per site, a pooling strategy will be considered as an option to be applied at the time of the Blinded Data Review Meeting.

In case there will be specific groups of Standard Of Care identified across sites, these will be grouped and the new stratification factor to consider for the analysis would become "Standard of Care". This option will be discussed during the Blind Data Review Meeting.

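### One imputed fit out of 1000 with a zero site variance removes site, the only named stratification factor, from the whole primary analysis

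*SAP*

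**What the plan says.** SAP 3.4.1.1 states "Randomization list will be stratified by site" and names no other factor. SAP 3.4.1 allocates patients "in a 1:1 ratio to either reparixin or placebo according to the stratified randomization list", in permuted blocks whose size is not given.

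The day 7 oxygenation index (OI) model in SAP 7.1.1.1 has treatment, baseline OI, gender and "age class (<65, >=65 years) as fixed effect and site as random effect". Section 7.1.1.2 uses the same structure for ventilator-free days (VFD), without a baseline value. After imputation, "Each of the 1000 datasets with observed and imputed data will be analyzed using the ANOVA model", and the results are combined by Rubin's rules.

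Both sections then give the fallback. The trigger reads "If convergence is not reached or the Estimated G-matrix is not positive definite in at least one of the models after imputation"; the consequence is that the random effect is dropped. Neither section puts another site adjustment in its place.

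The SAP knows that its sites are small: "Given the high number of sites and the relatively small number of patients per site, a pooling strategy will be considered as an option" for the blinded data review meeting (3.4.1.1, similarly 4.7). It gives no site count and does not link pooling to the fallback.

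**The concern.** The model has one variance component, so the G-matrix is that variance times an identity matrix. It fails to be positive definite exactly when the site variance is estimated as zero. With many small sites this is an ordinary outcome. It is also harmless, because the fit then coincides with the model without site. The rule nevertheless takes one such fit as a reason to remove site from the other 999, including those with a positive estimate.

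Three things follow:

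- The form of the primary model can turn on a single random draw, and more imputations make the loss of site more likely.
- The complete-case analysis (SAP 7.1.3.1) is a single fit without imputation, so it can keep site when the primary analysis has lost it. The two would then differ in model as well as in the handling of missing data. The missing-at-random (7.1.2.1), full analysis set (7.1.3.2) and per-protocol (7.1.3.3) analyses can diverge in the same way, although 7.1.3.3 takes extra steps to keep its estimates comparable with the randomized set.
- If sites really differ, leaving out a stratification factor makes the interval somewhat wider than it need be.

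**Working it through.** **Inputs from the documents.** 60 evaluable and about 66 enrolled, 1:1, 10% not evaluable (SAP 3.3); site-stratified permuted blocks (3.4.1, 3.4.1.1); 1000 fits (7.1.1.1, 7.1.1.2); two-sided 90% interval. **Assumed:** number and sizes of sites, ICC, blocks of 4, and the share of values imputed at random.

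**1. The plan's own precision figure.** SAP 3.3 gives a margin of at most 46.5% of the SD. The plain formula z(0.95) x sqrt(2/n) with n = 30 per arm gives 1.645 x 0.258 = 42.5%; with the t quantile it is 43.2%. The stated figure is larger, which could reflect an unstated assurance level (t with about 81% assurance gives 46.5%). 0.465 x 11.5 = 5.35 OI points, as stated; 0.465 x 8 = 3.72 days against 3.75 stated. None of this involves site, so 5.35 points and 3.75 days serve only as yardsticks below.

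**2. A zero-variance fit equals the no-site fit.** The covariance of the outcomes is s2 x I + t2 x ZZ', where t2 is the site variance. At t2 = 0 it is s2 x I, so the treatment estimate and its standard error are those of the model without site, apart from the degrees of freedom.

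**3. Why one in 1000 is an extreme trigger.** If a share p of imputed fits has zero variance and the draws are independent given the observed data, the rule fires with probability 1 - (1 - p)^1000. At p = 0.1% this is 1 - 0.999^1000 = 63%; at p = 0.3% it is 95%.

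**4. Simulation.** 66 patients, unequal sites, 1000 imputations by copy-reference or by a regression on 12 retrieved dropouts (copy-reference only in the 3% column), 200 trials per scenario (Monte Carlo error about 3 points: sqrt(0.67 x 0.33/200) = 0.033). The firing columns are for 20 and 30 sites; 3% is 2 patients. The last column also covers 10 sites and compares the pooled interval without and with site, only in trials where the rule fired.

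| ICC | Zero variance in one complete data set | Rule fires, 10% imputed | Rule fires, 3% imputed | Mean widening when it fires |
|---|---|---|---|---|
| 0 | about 55% | 93-100% | 78-85% | 0.4-1.4% |
| 0.05 | about 38% | 92-98% | 69% | 0.8-1.9% |
| 0.10 | about 24% | 85-95% | 61% | 1.2-2.7% |
| 0.20 | about 10% | 67-92% | 33-41% | 1.8-4.3% |
| 0.30 | about 4% | 51-84% | 18-23% | 2.8-6.0% |

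A separate run with 12-20 sites agrees. With 10% imputed, site was dropped in about 67-95% of trials at ICC 0-0.20, while 12-60% of individual fits had zero variance. With 3% imputed the rate at ICC 0.20 was 22-35%. Mean widening when the rule fired was under 1% at ICC 0 and about 1%, 1-2% and 2-4% at ICC 0.05, 0.10 and 0.20.

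**5. Size on the trial's scale.** For OI, 5.35 x 0.01 = 0.05 points and 5.35 x 0.04 = 0.21 points. For VFD, 3.75 x 0.04 = 0.15 days. The 95th percentile of widening across scenarios was about 2-15%, so at worst 5.35 x 0.15 = 0.80 points.

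**6. Validity.** On complete data the no-site 90% interval covered 89-93% at ICC 0, 0.10 and 0.20: nominal to slightly conservative.

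**The case against.** The best defence is that a fallback is prespecified, that one model across all imputed sets is tidy, and that little is at stake. The analyses are descriptive, and the rule fires mostly when the estimated site variance is close to zero, so site is lost most often when there is least to lose. If the software takes site out of the residual degrees of freedom, dropping it shrinks the t quantile by 0.3-1.4% and offsets part of the widening. All of this stands, and it keeps the point minor.

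The 10% is also weakly grounded. SAP 3.3 calls it the share not evaluable, not the share imputed at random. Deaths and extubations by day 7 receive fixed percentile values (4.4.1). VFD is set to 0 for death and is missing only for a patient who is alive and followed for fewer than 26 days (11.1.1). The 3% column may therefore be nearer the truth, above all for VFD, for which no separate simulation was run.

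A reader might infer three stronger things that the documents do not support:

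- *That site is certain to be lost.* This depends on the share imputed and on the ICC, and the documents fix neither.
- *That the interval is materially too wide.* Always ignoring a known site effect would cost up to 1/sqrt(1 - ICC) - 1, which is 2.6%, 5.4% and 11.8% at ICC 0.05, 0.10 and 0.20. The rule does not always ignore site; it fires selectively, and the conditional loss is well below those ceilings.
- *That a positive variance estimate proves a site effect.* At ICC 0 about 45% of complete data sets (100 - 55) still give one.

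Optional pooling does not settle the matter, because nothing ties it to the fallback.

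**Conclusion.** The rule works as read: one zero-variance fit in 1000 removes the only named stratification factor from a co-primary analysis. If about 10% of values are imputed at random across many small sites, this is likely (about 67-95% at ICC up to 0.20), and the any-one-of-1000 wording causes much of it. With few imputed values it is less likely (about 22-35% at ICC 0.20 with 3% imputed; 33-41% under the other site-size assumptions).

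The main fault is a primary model whose form depends on imputation draws and may not match its companion analyses. The effect on precision is slight conservatism, about 1%, 1-2% and 2-4% on average at ICC 0.05, 0.10 and 0.20 when the rule fires, with no real loss at ICC 0 and no sign of undercoverage. All these figures rest on assumed site counts, ICC, block size and imputed share. This is a worthwhile tidy-up and does not threaten the trial's conclusions.

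**What to change.** In SAP 7.1.1.1 and 7.1.1.2, replace the fallback by wording to this effect: site (or the pooled site factor, if one is adopted at the blinded review) stays as a random effect in every imputed fit; a zero site-variance estimate is accepted; a fit without site replaces only an individual imputed set whose model truly fails to converge; all 1000 results are pooled by Rubin's rules. Zero variance and non-convergence need separate treatment, because only the first is equivalent to the no-site model. State that the same rule governs both co-primary endpoints and the sensitivity and supplementary analyses, and report how many fits fell into each category.

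The cost is one sentence and a program flag. The downside is slightly fewer denominator degrees of freedom than if site were dropped.
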